5.7 Recruitment and Retention

5.7.1 Recruitment

Recruitment will be organised on a regional basis with the support of NIHR LCRNs. It is anticipated that 8 centres will each recruit 59 patients over 24 months. Each of the 8 centres is associated with an area with 200,000 people aged over 65. This corresponds to the area served by 14 to 20 consultants. The trial recruitment strategy focuses on three separate, complementary channels for recruitment with the aim that each site will recruit at least one case from each channel each recruitment month.

Clinicians working in the settings described below will be asked to identify potential patients to the site HTA-SYMBAD PI or research worker using a simple pro forma. On receipt of this information prior adherence to the AS/DH algorithm will be ascertained. Patients will not be excluded where they are referred into the trial through other mechanisms. The trial will be advertised on websites such as the Join Dementia Research website, which may also be a source of referral into the trial.

5.7.1.1 Recruitment strategy - Channel 1 – Community Mental Health Teams

Community mental health teams are the backbone of older people's mental health (OPMH) services and they are the team to which GPs are likely to refer people with BPSD. A catchment area of 200,000 will yield at least 200 referrals of people with dementia per month. At a conservative estimate, 20% will have BPSD that may require medication ie 40 potential cases per centre per month. It is acceptable to recruit both current cases and new referrals.

5.7.1.2 Recruitment strategy - Channel 2 - Care Homes

This an important group given the high level of agitation in care homes, the high use of antipsychotics there, and the fact that a third of people with dementia live in care homes. To support this channel CRN Division 4 will use its Enabling Research in Care Homes (ENRICH) Programme and the Research Ready Care Home Network. The network contains care home providers supportive of clinical research that wish to support local studies. It contains over 694 care homes across England and Scotland. These vary in size from 7 to 149 beds including larger corporate suppliers such as BUPA.

5.7.1.3 Recruitment strategy - Channel 3 - Memory Clinics

In all 8 sites there are memory clinics which are focused on early diagnosis and intervention in dementia. They initiate treatment and keep in contact with all cases that are initiated on antidementia drugs that are not passed on to community teams. These cases are reviewed on a six monthly basis and it is common for cases to have levels of agitated behaviours that would mean they were eligible for entry into this trial.

5.7.2 Retention

Participants and their carers will be followed up in their place of usual residence unless they request otherwise. Visit appointments will be made at previous visits.

5.8 Assignment of Intervention

5.8.1 Allocation

5.8.1.1 Sequence generation

Eligible, consented participants will be randomised on a 1:1:1 basis to one of three trial arms using a web based randomisation process, the randomisation scheme will be generated by the NCTU data manager. Allocation will be stratified by study region and independent living versus non-independent living. Independent living for the purposes of stratifying will mean participants living in their own home (even if this is assisted). Non-independent living will mean participants living in communal care/nursing homes.

Randomisation within strata will be based upon blocks of randomly varying block length (either 3 or 6).

5.8.1.2 Allocation concealment mechanism

At the point of randomisation the research worker will enter patient eligibility data into an online randomisation system. An immediate allocation will be provided by the system to the research worker, and a confirmatory email will be sent to the trial team, research worker, central site pharmacist and site PI. The allocated participant identification number will be recorded on a randomisation log that will periodically be sent to the co-ordinating centre as confirmation that the trial numbers allocated match the electronically stored data. Concealment of allocation will be guaranteed by using this central web based randomisation process.

5.8.1.3 Allocation Implementation

The PI is responsible for ensuring a participant is suitable to be randomised. In collaboration with the research worker, the PI will confirm eligibility and sign off the prescription of trial medication, according to the participant identification number allocated on randomisation. Each capsule pack will be identified by the participant identification number and trial details. Prior to making a trial dispensing visit the research worker will visit the central site pharmacy and pick up the treatment allocated. Accountability documentation will record the boxes with the participant identification numbers being dispensed from pharmacy to the research worker. This documentation will be updated when the research worker gives the trial medication to the participant/carer.

Only personnel who are named on the site delegation log will be permitted to confirm patient eligibility to join the study, sign off trial medication prescriptions and dispense trial medication to participants.

5.8.2 Blinding

The SYMBAD trial is intended to be a double blind trial and all non-statistical members of the trial team, their clinicians, participants and their carers will be blinded to trial arm allocation. To maintain the blind both active medications and the placebo will be identically encapsulated.

5.8.3 Unblinding

Final unblinding of all trial participants will not take place until after the creation of a locked analysis dataset.

The decision to unblind a single case should be made when knowledge of an individual's allocated treatment is required:

- · To enable treatment of severe adverse event/s, or
- $\cdot\,$ In the event of an overdose

Where possible, requests for emergency or unplanned unblinding of individuals should be made via the trial manager, and agreement of the Chief Investigator will then be sought. However, in

circumstances where there is insufficient time to make this request or for agreement to be sought, the treating clinician should make the decision to unblind immediately. This will be done via the study database (local PIs and the CI will have special logins which will allow unblinding and which will be closely audited within the database management system) or by contacting [name] who will authorise unblinding by the Data Management Team. All instances of unblinding should be recorded and reported to NCTU by the local principal investigator, including the identity of all recipients of the unblinding information.

5.9 Data Collection, Management and Analysis

5.9.1 Data Collection Methods

Data will be collected at the time-points indicated in the Trial Schedule (Section 5.3.4).

Research workers will complete paper CRFs during their visits to participants and their carers. They will then enter data onto a central database via an online system once they have internet access. Research workers will receive training on data collection and use of the online system. Identification logs, screening logs and enrolment logs will be kept locally, either in paper or electronic form.

Source data worksheets will be drafted by the data manager with the CI, trial statistician and PIs. These will be piloted and finalised. The database specification will be prepared by the NCTU data manager and approved by the CI and trial statistician prior to the database being built. The database will be prepared by the CTU data programmer and tested by the trial statistician and study site staff for user acceptability prior to the final system being launched.

Data collection, data entry and queries raised by a member of the HTA-SYMBAD trial team will be conducted in line with NCTU and trial specific Data Management Standard Operating Procedures.

Clinical trial team members will receive trial protocol training. All data will be handled in accordance with the Data Protection Act 1998.

5.9.2 Data Management

Within each trial site patients will be allocated a unique trial participant identification number (PIN). Data will be entered under this PIN onto the central database stored on the servers based at UEA. The database will be password protected and only accessible to members of the SYMBAD trial team at NCTU, the participating sites and external regulators. The server is in a secure room, which is protected by CCTV, where access is restricted to members of the UEA Information Systems team by security door access. The study database will be built using Microsoft SQL Server tools and direct access will be restricted to NCTU data management staff. Data entry will be via web pages created using Microsoft.NET technology. All internet traffic will be encrypted using the standard SSL (Secure Sockets Layer) methodology. The data entry system will validate data on entry to ensure it is of the expected type (e.g. integers, dates etc.) and range of values. Periodically and at database lock the data will be further validated for errors and inconsistencies. The database is linked to an audit tool where all data additions, modifications and deletions are recorded with date/time and the user ID of the person making the change. The database is designed to comply with the ICH Guideline for Good Clinical Practice (GCP), within the Standard Operating Procedures for Data Management in NCTU and also where appropriate with UEA IT procedures.

The database and coding values have been developed by the NCTU data manager in conjunction with the CI, study statistician and other NCTU members and the trial team. The database software provides a number of features to help maintain data quality, including; maintaining an audit trail, allowing custom validations on all data, allowing users to raise data query requests, and search facilities to identify validation failure/ missing data. Further details can be found in the SYMBAD Trial Data Management Plan. After completion of the trial the database will be retained on the servers of UEA for 15 years.

The identification, screening and enrolment logs, linking participant identifiable data to the PIN, will be held locally by the research sites and potentially at NCTU. This will either be held in written form in a locked filing cabinet or electronically in password protected form on hospital computers. After completion of the trial the identification, screening and enrolment logs will be stored securely by the sites for a minimum of 15 years.

5.9.3 Non-Adherence and Non-Retention

The consent form will explain that if a participant wishes to withdraw from the study the data acquired prior to that point will be retained. Reason for withdrawal will be recorded, if given, as will loss to follow up.

Non adherence to trial medication will be assessed through capsule counts of unused returned drug supplies and review of the diary card at each study visit.

5.9.4 Statistical Methods

Primary analyses will compare mirtazapine with placebo and carbamazepine with placebo on CMAI score at 12 weeks post randomisation. Analyses of clinical effectiveness will be pragmatic using linear mixed modelling, based on the Intention to Treat (ITT) population with all available follow-up data from all randomized patients controlling for baseline levels of agitation and centre. Secondary cost-effectiveness analyses will be conducted from societal and health and social care perspectives and will compare comprehensive costs with CMAI change.

Analyses will be on an ITT basis so each patient will be defined by their randomisation group at recruitment. The primary ITT analysis is intended to provide inferences regarding the effectiveness of the intervention overall: not to provide inferences regarding the causal effect of the intervention itself, but on the intervention as deployed in 'real life'. So compliance information is not necessary to ensure that the 'intention to treat' analysis is valid. The sample size is adjusted for up to a 15% drop out at 12 weeks.

5.9.4.1 Statistical Analysis Plan

A full Statistical Analysis Plan (SAP) will be developed between the trial statistician and Chief Investigator and agreed with the trial's governance committees.

All cause withdrawal from randomised treatment will be reported. The prevalence of specific adverse events and reactions will be reported descriptively at weeks 6 and 12. The prevalence of patients experiencing one or more serious adverse events will be compared at 6 and 12 weeks post randomisation across the three trial arms (as randomised) using Chi Square tests conditional on evidence of effectiveness of one IMP over placebo. Mortality prevalence will be considered independently of any other serious adverse events.

The primary analyses will be with regard to placebo v carbamazepine and placebo v mirtazapine. However, carbamazepine v mirtazapine comparisons of efficacy and adverse effects will also be carried out as a secondary analysis. These will follow the same approach as above though the study sample size has not been selected with this comparison in mind, and any differences in efficacy are likely to be small compared to differences from placebo.

After the 12 week period of randomised treatment has finished, long term outcomes in terms of CMAI score, treatment state, institutionalisation and death will be completed at 26 and 52 weeks. The 6 and 12 week analyses will be reported separately once these have been completed to ensure no delay in communicating the primary outcomes of the study. The long term follow up data from 26 and 52 weeks will be collated at the CDS, linked to the prior data and analysed and reported separately once the core study has been completed.

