in patients taking carbamazepine. Blood counts including platelets and reticulocytes will be taken at baseline and after 12 weeks of dosing. Further blood tests may be ordered during the trial if clinically indicated.

There is a well-recognised risk of drug interactions which will be managed by increased monitoring or through exclusion of some categories of drugs, as listed in the exclusion criteria.

An increase in suicidal thoughts has been observed as a rare effect in the early stages of treatment with antidepressants. We have therefore included the Columbia Suicide Severity Rating Scale (C-SSRS) at baseline and at the 6 and 12 week assessment timepoints to monitor this, again the PI will have access to these data following baseline assessment and from subsequent visits. Hyponatraemia is also a recognised rare side effect of antidepressant medication and the baseline and 12 week U&Es will allow us to monitor this.

4.2 **Objectives**

The overall trial aim is to assess the safety, clinical and cost effectiveness of mirtazapine and carbamazepine in the treatment of agitation in dementia.

The null hypothesis is that there is no difference in CMAI scores between patients treated with placebo and mirtazapine, and between patients treated with placebo and carbamazepine, at 12 weeks.

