4.2.2 Secondary objectives

Each drug is assessed independently, thus the secondary objectives are:

- 1 To determine if mirtazapine and carbamazepine are more cost-effective than placebo at 12 weeks post randomisation,
- 2 To determine if mirtazapine and carbamazepine are more clinically and cost effective than placebo in reducing CMAI score at 6 weeks post randomisation,
- 3 To determine differences in effectiveness between mirtazapine and carbamazepine and placebo on carers,
- 4 To determine whether there are differences between the groups in adverse events and adherence,
- 5 To determine differences between carbamazepine and mirtazapine in effect on agitation by CMAI score 6 and 12 weeks post randomisation and in adverse events and adherence, conditional on evidence of effectiveness of one IMP over placebo,
- 6 To determine long term differences between those randomised to placebo, carbamazepine and mirtazapine in three way head-to-head comparisons of agitation (measured by CMAI score), institutionalisation, death and clinical management at 26 and 52 weeks postrandomisation.

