5.5.2 Secondary Outcomes

- 1 Costs derived from Client Service Receipt Inventory (CSRI), and QALYs from cost data alongside supplemented information from DEMQOL and EQ-5D-5L interviews 12 weeks post randomisation.
- 2 Cohen Mansfield Agitation Inventory (CMAI) score and cost at 6 weeks post randomisation.
- 3 Patient and carer quality of life, and carer outcomes at 6 and 12 weeks post randomisation.
- 4 Adverse events from week 0 to week 16 and adherence at 6 and 12 weeks post randomisation.
- 5 CMAI score, adverse events and adherence at 6 and 12 weeks, conditional on evidence of effectiveness of one IMP over placebo.
- 6 Longer term follow up: CMAI score, institutionalisation, death and clinical management at 26 and 52 weeks post-randomisation.

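### The only planned formal treatment-period comparison of serious adverse events that includes placebo is run only if one drug proves effective, which contradicts the unconditional safety aim, objective 4 and outcome 4

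*Protocol*

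**What the plan says.** Section 5.9.4.2 of the Protocol plans one formal analysis of SAEs. The proportion of patients with one or more SAEs "will be compared at 6 and 12 weeks post randomisation across the three trial arms (as randomised"), and the sentence ends "using Chi Square tests conditional on evidence of effectiveness of one IMP over placebo". Placebo is one of the three arms, so the comparison of each drug with placebo falls under the condition. Other adverse event data are handled differently: "The prevalence of specific adverse events and reactions will be reported descriptively at weeks 6 and 12".

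Elsewhere the protocol separates two safety questions.

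- **Unconditional.** Section 4.2 opens: "The overall trial aim is to assess the safety, clinical and cost effectiveness of mirtazapine and carbamazepine". Secondary objective 4 in 4.2.2 is "To determine whether there are differences between the groups in adverse events and adherence". Secondary outcome 4 in 5.5.2 is "Adverse events from week 0 to week 16 and adherence at 6 and 12 weeks post randomisation".
- **Conditional.** Objective 5, which is limited to carbamazepine versus mirtazapine, asks about differences "in adverse events and adherence, conditional on evidence of effectiveness of one IMP over placebo". Outcome 5 is its counterpart: "CMAI score, adverse events and adherence at 6 and 12 weeks, conditional on evidence of effectiveness of one IMP over placebo".

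**The concern.** The condition attached to objective 5 and outcome 5 reappears in 5.9.4.2 on the three-arm SAE test, which is the analysis that would serve objective 4. The later paragraph of 5.9.4.2 on carbamazepine versus mirtazapine, where objective 5 would put the condition, states none. The clause seems to sit on the wrong comparison.

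Whether a drug causes more serious events than placebo does not depend on whether it reduces agitation. Section 4.1.5 notes that both drugs are already in common use in older people, including people with dementia, so harm without benefit is a result that prescribers would need. Under the stated rule it would normally go without a formal comparison. The condition also requires effectiveness of one IMP only, so whether one drug's SAEs are tested against placebo can turn on the efficacy of the other drug.

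**Working it through.** **Inputs, all from Protocol 5.6 and 5.9.4.2.** Difference of 6 CMAI points, SD 15, two-sided 5% tests, 90% power, 1:1:1 allocation, 400 evaluable, 15% attrition, 471 randomised (157 per arm), no multiplicity adjustment.

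**Reproducing the stated sample size.** n per arm = 2(1.960 + 1.282)² × 15²/6² = 131.3, rounded up to 132. That is 396 in total, against 400 stated. 400/0.85 = 470.6, giving 471 = 3 × 157. With 400/3 per arm the standard error of a difference is 15√(2/133.3) = 1.837. Power at 6 points is then Φ(6/1.837 − 1.960) = Φ(1.306) = 90.4%. The plan's figures hold.

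**How often the SAE test would be run.** The protocol does not define evidence of effectiveness. Assume it means a favourable two-sided p<0.05 for at least one drug. The two drug-placebo Z statistics share the placebo arm: their covariance is σ²/n and each variance is 2σ²/n, so their correlation is 0.5. With μ = true effect/1.837,

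P(test is run) = 1 − Φ₂(1.960 − μ₁, 1.960 − μ₂; ρ = 0.5).

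| True effects (CMAI points) | P(SAE test is run) |
|---|---|
| 0 and 0 | 4.5% |
| 3 and 0 | 37.6% |
| 3 and 3 | 52.9% |
| 6 and 0 | 90.4% |
| 6 and 6 | 97.0% |

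If significance in either direction opened the test, the null figure would be 9.1%. So between about 91% and 95.5% of trials in which neither drug works would make no formal SAE comparison.

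**What an unconditional test could detect.** The protocol gives no SAE rates, so these are assumptions. For a pairwise test with n = 157 per arm,

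power = Φ{[|p₁ − p₀| − 1.960√(2p̄(1 − p̄)/n)] / √[(p₀(1 − p₀) + p₁(1 − p₁))/n]}.

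| Placebo v drug | Power |
|---|---|
| 5% v 10% | 0.390 |
| 20% v 30% | 0.535 |
| 10% v 20% | 0.701 |
| 5% v 15% | 0.843 |

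The planned test is a three-arm chi-square on 2 df, with noncentrality n Σ(pᵢ − p̄)²/[p̄(1 − p̄)]. With one arm raised, its power is 0.434 for 5%, 5%, 10%, then 0.773 for 10%, 10%, 20%, and 0.923 for 5%, 5%, 15%. If neither drug works, the conditional procedure cannot detect any of these differences in more than 4.5% of trials, because the test is run no more often than that (9.1% on the either-direction reading).

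**The case against.** A reader might infer that nothing in the plan compares harm with placebo, or that a negative trial would leave safety unreported. The documents do not support either reading.

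- Specific adverse events and reactions, and all-cause withdrawal from treatment, are reported in 5.9.4.2 whatever the efficacy result. SAE counts by arm might well be visible in those tables.
- Mortality is taken out of the SAE sentence and considered separately, although no method is given.
- Objective 6 compares death across all three arms at 26 and 52 weeks without condition.
- Comparisons of adverse effects between the two active drugs are also planned.
- The IDMC sees unblinded safety data by arm (5.10.2) and can advise on continuation (5.10.3.4.4).

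These points limit the scope but do not remove the contradiction. The descriptive tables contain no planned comparison. The death comparison is made 14 and 40 weeks after the 12-week treatment period and covers one event type. The active-versus-active analysis leaves out placebo. IDMC review is monitoring during the trial, not a final analysis.

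It can also be argued that 5.9.4.2 has secondary outcomes follow the primary approach, with a treatment term in each model, and that adverse events are secondary outcome 4. That is a general statement about linear models. The SAE sentence is specific, names its own test and sets its own condition, so it would be expected to govern.

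The clause may be a drafting slip. That makes the correction easy but does not make the text right. Nor is this a detail left to the SAP: the protocol states the rule. A SAP that followed it would leave objective 4 without a formal SAE test in most negative trials, and one that did not would depart from the protocol.

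Finally, the primary efficacy estimate, the type I error, the sample size and the data collected are unaffected. That stands.

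**Conclusion.** The text of 5.9.4.2 is wrong as written. It makes the only planned formal treatment-period comparison of SAEs that includes placebo depend on efficacy, while the aim, objective 4 and outcome 4 are unconditional. What is lost is that formal comparison, not the safety data as a whole.

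The test would be run in about 4.5% of trials if neither drug works (about 9% if either direction counts), about 38% if one drug has a 3-point effect, and 90% if one has the design effect of 6 points. These figures rest on reading the undefined condition as p<0.05 for at least one drug, on about 133 analysed per arm, and on the planning SD of 15. The contradiction itself rests on none of these assumptions. The power of an unconditional pairwise test, roughly 39% to 84% over the rates shown, depends wholly on assumed SAE rates and only illustrates what is given up.

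**What to change.** In 5.9.4.2, end the SAE sentence at the chi-square tests and delete the conditional clause that follows. State that patients with one or more SAEs will be compared between each drug and placebo whatever the efficacy result, so that objective 4 and outcome 4 are answered. Keep any such condition only for the carbamazepine-versus-mirtazapine comparison in objective 5. If it is kept there, repeat it in the 5.9.4.2 paragraph on that comparison and say what counts as evidence of effectiveness.

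Preferably, report each difference from placebo with a 95% confidence interval beside the chi-square result. With 157 per arm and equal rates, the half-width is 1.96√(2p(1 − p)/157), about 4.8 points at an assumed SAE rate of 5% and 6.6 points at 10%. This is a reporting preference and separate from the contradiction.

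The cost is one amended sentence and a short table from data already collected. If a SAP exists, its SAE section should be aligned with the amended sentence.
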